APPENDIX 4 WOMEN OF CHILDBEARING POTENTIAL DEFINITIONS AND METHODS OF CONTRACEPTION

DEFINITIONS

Woman of Childbearing Potential (WOCBP)

A woman is considered fertile following menarche and until becoming post-menopausal unless permanently sterile. Permanent sterilization methods include hysterectomy, bilateral salpingectomy, and bilateral oophorectomy.

Women in the following categories are not considered WOCBP

- Premenarchal
- Premenopausal female with 1 of the following:
 - Documented hysterectomy
 - Documented bilateral salpingectomy
 - Documented bilateral oophorectomy

Note: Documentation can come from the site personnel's review of the participant's medical records, medical examination, or medical history interview.

- Postmenopausal female
 - A postmenopausal state is defined as 12 months of amenorrhea in a woman over age 45 years in the absence of other biological or physiological causes. In addition, females under the age of 55 years must have a serum follicle stimulating hormone, (FSH) level > 40 mIU/mL to confirm menopause.

CONTRACEPTION GUIDANCE FOR FEMALE PARTICIPANTS OF CHILD BEARING POTENTIAL

One of the highly effective methods of contraception listed below is required during study duration and until the end of relevant systemic exposure, defined as 5 months after the end of study treatment.*

Highly Effective Contraceptive Methods That Are User Dependent
Failure rate of <1% per year when used consistently and correctly.^a

• Combined (estrogen- and progestogen-containing) hormonal contraception associated with inhibition of ovulation^b
– oral– intravaginal– transdermal

• Progestogen-only hormonal contraception associated with inhibition of ovulation^b
– oral– injectable

Highly Effective Methods That Are User Independent

 • Implantable progestogen-only hormonal contraception associated with inhibition of ovulation^b • Intrauterine hormone-releasing system (IUS)^c • Intrauterine device (IUD)^c • Bilateral tubal occlusion

 • Vasectomized partner 
A vasectomized partner is a highly effective contraception method provided that the partner is the sole male sexual partner of the WOCBP and the absence of sperm has been confirmed. If not, an additional highly effective method of contraception should be used.


 • Sexual abstinence 
Sexual abstinence is considered a highly effective method only if defined as refraining from heterosexual intercourse during the entire period of risk associated with the study drug. The reliability of sexual abstinence needs to be evaluated in relation to the duration of the study and the preferred and usual lifestyle of the participant.
 
 • It is not necessary to use any other method of contraception when complete abstinence is elected. • WOCBP participants who choose complete abstinence must continue to have pregnancy tests, as specified in Section 2. • Acceptable alternate methods of highly effective contraception must be discussed in the event that the WOCBP participants chooses to forego complete abstinence

NOTES:
 
^a Typical use failure rates may differ from those when used consistently and correctly. Use should be consistent with local regulations regarding the use of contraceptive methods for participants participating in clinical studies.
 
^b Hormonal contraception may be susceptible to interaction with the study drug, which may reduce the efficacy of the contraceptive method. Hormonal contraception is permissible only when there is sufficient evidence that the IMP and other study medications will not alter hormonal exposures such that contraception would be ineffective or result in increased exposures that could be potentially hazardous. In this case, alternative methods of contraception should be utilized.
 
^c Intrauterine devices and intrauterine hormone releasing systems are acceptable methods of contraception in the absence of definitive drug interaction studies when hormone exposures from intrauterine devices do not alter contraception effectiveness

Unacceptable Methods of Contraception*

 • Male or female condom with or without spermicide. Male and female condoms cannot be used simultaneously • Diaphragm with spermicide • Cervical cap with spermicide • Vaginal Sponge with spermicide • Progestogen-only oral hormonal contraception, where inhibition of ovulation is not the primary mechanism of action

- Periodic abstinence (calendar, symptothermal, post-ovulation methods)
- Withdrawal (coitus interruptus).
- Spermicide only
- Lactation amenorrhea method (LAM)

*** Local laws and regulations may require use of alternative and/or additional contraception methods.**

NOT APPLICABLE PER PROTOCOL AMENDMENT 04: CONTRACEPTION GUIDANCE FOR MALE PARTICIPANTS WITH PARTNER(S) OF CHILD BEARING POTENTIAL.

Male participants with female partners of childbearing potential are eligible to participate if they agree to the following during the treatment and until the end of relevant systemic exposure.

- Inform any and all partner(s) of their participation in a clinical drug study and the need to comply with contraception instructions as directed by the investigator.
- Male participants are required to use a condom for study duration and until end of relevant systemic exposure defined as 7 months after the end of study treatment.
- Female partners of males participating in the study to consider use of effective methods of contraception until the end of relevant systemic exposure, defined as 7 months after the end of treatment in the male participant.
- Male participants with a pregnant or breastfeeding partner must agree to remain abstinent from penile vaginal intercourse or use a male condom during each episode of penile penetration during the treatment and until 7 months after the end of study treatment.
- Refrain from donating sperm for the duration of the study treatment and until 7 months after the end of study treatment.

COLLECTION OF PREGNANCY INFORMATION

Guidance for collection of Pregnancy Information and outcome of pregnancy on the Pregnancy Surveillance Form is provided in [Section 9.2.5](#) and the Appendix for Adverse Events and Serious Adverse Events Definitions and procedures for Evaluating, Follow-up and Reporting

APPENDIX 5 MANAGEMENT ALGORITHMS FOR STUDIES UNDER CTCAE VERSION 5.0

These general guidelines constitute guidance to the Investigator and may be supplemented by discussions with the Medical Monitor representing the Sponsor. The guidance applies to all immuno-oncology agents and regimens.

A general principle is that differential diagnoses should be diligently evaluated according to standard medical practice. Non-inflammatory etiologies should be considered and appropriately treated.

[figure not shown]
Corticosteroids are a primary therapy for immuno-oncology drug-related adverse events. The oral equivalent of the recommended IV doses may be considered for ambulatory patients with low-grade toxicity. The lower bioavailability of oral corticosteroids should be taken into account when switching to the equivalent dose of oral corticosteroids.

Consultation with a medical or surgical specialist, especially prior to an invasive diagnostic or procedure, is recommended.

The frequency and severity of the related adverse events covered by these algorithms will depend on the immuno-oncology agent or regimen being used.

GI Adverse Event Management Algorithm

Rule out non-inflammatory causes. If non-inflammatory cause is identified, treat accordingly and continue I-O therapy.
Opiates/narcotics may mask symptoms of perforation. Infliximab should not be used in cases of perforation or sepsis.

[figure not shown]
Patients on IV steroids may be switched to an equivalent dose of oral corticosteroids (eg, prednisone) at start of tapering or earlier, after sustained clinical improvement is observed. Lower bioavailability of oral corticosteroids should be taken into account when switching to the equivalent dose of oral corticosteroids.

* Discontinue for Grade 4 diarrhea or colitis. For Grade 3 diarrhea or colitis, 1) Nivolumab monotherapy: Nivolumab can be delayed. 2) Nivolumab+ Ipilimumab combination: Ipilimumab should be discontinued while nivolumab can be delayed. Nivolumab monotherapy can be resumed when symptoms improve to Grade 1. Please refer to protocol for dose delay and discontinue criteria for other combinations.

28-Sep-2020

Renal Adverse Event Management Algorithm

Rule out non-inflammatory causes. If non-inflammatory cause, treat accordingly and continue I-O therapy.

[figure not shown]

Patients on IV steroids may be switched to an equivalent dose of oral corticosteroids (eg, prednisone) at start of tapering or earlier, after sustained clinical improvement is observed. Lower bioavailability of oral corticosteroids should be taken into account when switching to the equivalent dose of oral corticosteroids.

28-Sep-2020

Pulmonary Adverse Event Management Algorithm

Rule out non-inflammatory causes. If non-inflammatory cause, treat accordingly and continue I-O therapy.
Evaluate with imaging and pulmonary consultation.

[figure not shown]

Patients on IV steroids may be switched to an equivalent dose of oral corticosteroids (eg, prednisone) at start of tapering or earlier, after sustained clinical improvement is observed. Lower bioavailability of oral corticosteroids should be taken into account when switching to the equivalent dose of oral corticosteroids.

28-Sep-2020

Hepatic Adverse Event Management Algorithm

Rule out non-inflammatory causes. If non-inflammatory cause, treat accordingly and continue I-O therapy.
Consider imaging for obstruction.

Patients on IV steroids may be switched to an equivalent dose of oral corticosteroids (e.g. prednisone) at start of tapering or earlier, after sustained clinical improvement is observed. Lower bioavailability of oral corticosteroids should be taken into account when switching to the equivalent dose of oral corticosteroids.

[figure not shown]
^Λ Please refer to protocol dose delay and discontinue criteria for specific details.

*The recommended starting dose for AST or ALT > 20 x ULN or bilirubin >10 x ULN is 2 mg/kg/day methylprednisolone IV.

28-Sep-2020

Endocrinopathy Adverse Event Management Algorithm

Rule out non-inflammatory causes. If non-inflammatory cause, treat accordingly and continue I-O therapy.
Consider visual field testing, endocrinology consultation, and imaging.

[figure not shown]

Patients on IV steroids may be switched to an equivalent dose of oral corticosteroids (eg, prednisone) at start of tapering or earlier, after sustained clinical improvement is observed. Lower bioavailability of oral corticosteroids should be taken into account when switching to the equivalent dose of oral corticosteroids.

28-Sep-2020

Skin Adverse Event Management Algorithm

Rule out non-inflammatory causes. If non-inflammatory cause, treat accordingly and continue I-O therapy.

Patients on IV steroids may be switched to an equivalent dose of oral corticosteroids (e.g. prednisone) at start of tapering or earlier, after sustained clinical improvement is observed. Lower bioavailability of oral corticosteroids should be taken into account when switching to the equivalent dose of oral corticosteroids.

[figure not shown]
*Refer to NCI CTCAE v5 for term-specific grading criteria.

^If Steven-Johnson Syndrome (SJS), toxic epidermal necrosis (TEN), Drug Reaction with Eosinophilia and Systemic Symptoms (DRESS) is suspected, withhold I-O therapy and refer patient for specialized care for assessment and treatment. If SJS, TEN, or DRESS is diagnosed, permanently discontinue I-O therapy.

28-Sep-2020

Neurological Adverse Event Management Algorithm

Rule out non-inflammatory causes. If non-inflammatory cause, treat accordingly and continue I-O therapy.

[figure not shown]
Patients on IV steroids may be switched to an equivalent dose of oral corticosteroids (eg. prednisone) at start of tapering or earlier, after sustained clinical improvement is observed. Lower bioavailability of oral corticosteroids should be taken into account when switching to the equivalent dose of oral corticosteroids.

[^]Discontinue for any grade myasthenia gravis, Guillain-Barre syndrome, treatment-related myelitis, or encephalitis.

28-Sep-2020

Myocarditis Adverse Event Management Algorithm

Rule out non-inflammatory causes. If non-inflammatory cause, treat accordingly and continue I-O therapy.

Patients on IV steroids may be switched to an equivalent dose of oral corticosteroids (eg, prednisone) at start of tapering or earlier, after sustained clinical improvement is observed. Lower bioavailability of oral corticosteroids should be taken into account when switching to the equivalent dose of oral corticosteroids. Prophylactic antibiotics should be considered in the setting of ongoing immunosuppression.

28-Sep-2020

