7.4.1 Dose Delay Criteria

Delay administration of both nivolumab and ipilimumab if any of the delay criteria in [Section 7.4.1](#) are met. Delay nivolumab and ipilimumab dosing for any adverse event, laboratory abnormality, or intercurrent illness which, in the judgment of the investigator, warrants delaying the dose of study medication.

Delay dosing for severe acute respiratory syndrome coronavirus 2 (SARS-CoV-2) infection, either confirmed or suspected.

For participants who require delay of nivolumab and ipilimumab, re-evaluate weekly or more frequently if clinically indicated and resume dosing when criteria to resume treatment are met (see [Section 7.4.2](#)).

Continue tumor assessments per protocol even if dosing is delayed.

Table 7.4.1-1: Adverse Event Criteria for Delay, Resumption, and Discontinuation of Nivolumab and Ipilimumab

Drug-related Adverse Event (AE) per CTCAE V5	Severity	Action Taken	Clarifications, Exceptions, and Resumption Criteria
Gastrointestinal			
Colitis or diarrhea	Grade 2	Delay dose	Dosing may resume when AE resolves to baseline.
	Grade 3	Nivolumab monotherapy: Delay dose	Dosing may resume when AE resolves to baseline.
		When administered with ipilimumab: Permanently discontinue ipilimumab	Nivolumab monotherapy may be resumed when AE resolves to baseline. If Grade 3 diarrhea or colitis recurs while on nivolumab monotherapy, permanently discontinue.
	Grade 4	Permanently discontinue	
Renal			
Serum creatinine increased	Grade 2 or 3	Delay dose	Dosing may resume when AE resolves to Grade \leq 1 or baseline value.
	Grade 4	Permanently discontinue	
Pulmonary			
Pneumonitis	Grade 2	Delay dose	Dosing may resume after pneumonitis has resolved to Grade \leq 1.
	Grade 3 or 4	Permanently discontinue	
Hepatic			
Aspartate aminotransferase (AST), alanine aminotransferase (ALT), or total bilirubin (T.bili) increased	AST or ALT $> 3\times$ and $\leq 5\times$ upper limit of normal (ULN) or T.bili $> 1.5\times$ and $\leq 3\times$ ULN, regardless of baseline value	Delay dose	Dosing may resume when laboratory values return to baseline.
	AST or ALT $> 5 \times$ ULN or T. bili $> 3 \times$ ULN, regardless of baseline value	Delay dose or permanently discontinue	In most cases of AST or ALT $> 5\times$ ULN, study treatment will be permanently discontinued. If the investigator determines a possible favorable benefit/risk ratio that warrants continuation of study

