Pancreatitis: Amylase or lipase increased	Grade 3 with symptoms	Delay dose	Note: Grade 3 increased amylase or lipase without signs or symptoms of pancreatitis does not require dose delay. Dosing may resume when patient becomes asymptomatic.
	Grade 4	Permanently discontinue	
Uveitis	Grade 2 uveitis	Delay dose	Dosing may resume if uveitis responds to topical therapy (eye drops) and after uveitis resolves to Grade ≤ 1 or baseline. If patient requires oral steroids for uveitis, then permanently discontinue study drug.
	Grade 3 or 4 uveitis	Permanently discontinue	
Other drug-related AE (not listed above)	Grade 2 non-skin AE, except fatigue	Delay dose	Dosing may resume when AE resolves to Grade ≤ 1 or baseline value.
	Grade 3 AE - First occurrence lasting ≤ 7 days	Delay dose	Dosing may resume when AE resolves to Grade ≤ 1 or baseline value.
	Grade 3 AE - First occurrence lasting > 7 days	Permanently discontinue	

Table 7.4.1-1: Adverse Event Criteria for Delay, Resumption, and Discontinuation of Nivolumab and Ipilimumab

Drug-related Adverse Event (AE) per CTCAE V5	Severity	Action Taken	Clarifications, Exceptions, and Resumption Criteria
	Recurrence of Grade 3 AE of any duration	Permanently discontinue	
	Grade 4 or life-threatening adverse reaction	Permanently discontinue	
Other Laboratory Abnormalities			
Other drug-related laboratory abnormality (not listed above)	Grade 3	Delay dose	Exceptions: No delay required for: Grade 3 lymphopenia Permanent discontinuation for: Grade 3 thrombocytopenia > 7 days or associated with bleeding
	Grade 4	Permanently discontinue	Exceptions: The following events do not require discontinuation of study drug: 
 • Grade 4 neutropenia ≤ 7 days • Grade 4 lymphopenia or leukopenia • Grade 4 isolated electrolyte imbalances/abnormalities that are not associated with clinical sequelae and are responding to supplementation/appropriate management within 72 hours of their onset
Infusion Reactions (manifested by fever, chills, rigors, headache, rash, pruritus, arthralgia, hypotension, hypertension, bronchospasm, or other allergic-like reactions)			
Hypersensitivity reaction or infusion reaction	Grade 3 or 4	Permanently discontinue	Refer to Section 7.4.4 .

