7.4.2 Criteria to Resume Treatment

Participants may resume treatment with study drug if they have completed AE management (ie, corticosteroid taper) or are on ≤ 10 mg prednisone or equivalent and meet the requirements per Table 7.4.1-1.

Participants with SARS-CoV-2 infection (either confirmed or suspected) may resume treatment after **all of the following**:

- 1) At least 10 days (20 days for severe/critical illness) have passed since symptoms first appeared or positive test result (e.g. reverse transcription polymerase chain reaction [RT-PCR] or viral antigen),
- 2) Resolution of acute symptoms (including at least 24 hours have passed since last fever without fever reducing medications),
- 3) Evaluation by the Investigator with confirmation that there are no sequelae that would place the participant at a higher risk of receiving investigational treatment, **and**
- 4) Consultation by the medical monitor.

For suspected cases, treatment may also resume if SARS-CoV-2 infection is ruled-out and other criteria to resume treatment are met. Prior to re-initiating treatment in a participant with a dosing delay lasting > 6 weeks for nivolumab or > 12 weeks for ipilimumab, the Medical Monitor (or designee) must be consulted. Continue tumor assessments per protocol even if dosing is delayed. Continue periodic study visits to assess safety and laboratory studies every 6 weeks or more frequently if clinically indicated during such dosing delays.

When criteria to resume treatment are met, resume both nivolumab and ipilimumab on the same day unless the investigator determines that one of the agents must be discontinued due to toxicity attributed to that agent alone.

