7.4.5 Management Algorithms for Immuno-oncology Agents

Immuno-oncology (IO) agents are associated with AEs that can differ in severity and duration from AEs caused by other therapeutic classes. Nivolumab and ipilimumab are considered IO

agents, and the management algorithms in [Appendix 5](#) provide guidance on assessing and managing the following groups of AEs:

- Gastrointestinal
- Renal
- Pulmonary
- Hepatic
- Endocrinopathy
- Skin
- Neurological
- Myocarditis

Treatment management algorithms are found in the nivolumab IB⁴⁷ and in [Appendix 5](#).

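### After Grade 3 diarrhea or colitis on the combination, the Appendix 5 GI footnote lets nivolumab restart at Grade 1, while Table 7.4.1-1 requires return to baseline

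*Combined protocol and SAP*

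**What the plan says.** Table 7.4.1-1 (Section 7.4.1) covers Grade 3 colitis or diarrhea when nivolumab is given with ipilimumab. Ipilimumab is stopped permanently, and "Nivolumab monotherapy may be resumed when AE resolves to baseline". The same cell adds that a recurrence at Grade 3 on nivolumab alone ends treatment for good.

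Section 7.4.2 gives this table its force. To resume, a participant must have completed management of the event or be on no more than 10 mg of "prednisone or equivalent and meet the requirements per Table 7.4.1-1".

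The footnote to the gastrointestinal algorithm in Appendix 5 addresses the same event on the same regimen. It says "Ipilimumab should be discontinued while nivolumab can be delayed", and then "Nivolumab monotherapy can be resumed when symptoms improve to Grade 1". It ends: "Please refer to protocol for dose delay and discontinue criteria for other combinations".

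Appendix 5 opens by calling its content guidance. Section 7.4.5 describes it in the same way: the algorithms "provide guidance on assessing and managing the following groups of AEs", and gastrointestinal events head the list that follows.

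**The concern.** Two current texts set different restart thresholds for one event on one of the trial's own regimens, and the more permissive text sits where the protocol sends investigators to manage that event. A participant who was free of diarrhea at baseline and has improved to Grade 1 may be re-dosed under the footnote but not under the table.

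The consequence concerns safety and conduct. A site could re-expose a participant to nivolumab too early after a severe, possibly immune-mediated event, and would deviate from the protocol while following the sponsor's own appendix. Section 9 allows no waivers. Gastrointestinal toxicity is foreseeable on this regimen: Section 3.2.3 reports treatment-related gastrointestinal select events in 23% of patients on nivolumab 3 mg/kg every 2 weeks plus ipilimumab 1 mg/kg every 6 weeks in CA209012. That figure covers all grades, so it shows relevance and does not estimate how many participants would be affected here.

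**Working it through.** No formula or planning figure is involved. The check sets the two rules side by side.

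**1. Same event, same regimen.** Both texts concern Grade 3 diarrhea or colitis on nivolumab plus ipilimumab. Both stop ipilimumab, hold nivolumab and contemplate nivolumab alone afterwards. Both discontinue at Grade 4. They differ only in the threshold for restarting nivolumab.

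**2. Are the two thresholds really different?** Within Table 7.4.1-1 they are. Where the table accepts residual Grade 1 toxicity, it says so. The row for other drug-related events reads "Dosing may resume when AE resolves to Grade ≤ 1 or baseline value", and the serum creatinine, hyperglycemia and uveitis rows offer the same alternative. The colitis/diarrhea row names baseline alone, at Grade 2 and at Grade 3. Baseline in that row therefore cannot be read as shorthand for Grade 1.

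**3. Which text governs?** Section 7.4.2 makes Table 7.4.1-1 a requirement for resuming. Appendix 5 is guidance by its own description. The table governs.

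**4. Does the footnote send the reader back to the table?** Not for this regimen. Its closing referral covers other combinations only, so a reader would take nivolumab plus ipilimumab as settled by the footnote.

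**5. Where do the rules diverge?** Assume a baseline of Grade 0 or 1:

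| Baseline grade | Current grade | Footnote | Table 7.4.1-1 |
|---|---|---|---|
| 0 | 0 | restart allowed | restart allowed |
| 0 | 1 | restart allowed | **not allowed** |
| 1 | 0 | restart allowed | restart allowed |
| 1 | 1 | restart allowed | restart allowed |
| 0 or 1 | 2 or higher | not allowed | not allowed |

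The rules part in one state: baseline Grade 0, now Grade 1. The grid lists possible states and says nothing about how often each occurs. Within it the footnote is never the stricter rule, so waiting for baseline always satisfies both texts. The direction would reverse only for a baseline of Grade 2 or worse, which is outside this assumption.

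**6. Is the text current?** Yes. The algorithm is dated 28-Sep-2020. The Amendment 04 summary says that both the dose criteria and Appendix 5 were updated to align with the Investigator Brochure, yet the two still differ.

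**The case against.** The strongest reply is that the protocol already settles the matter. Section 7.4.2 ties resumption to the table, Section 9 forbids waivers, and Appendix 5 is generic guidance written for all immuno-oncology agents. On that view the footnote is a loose line in a subordinate text, and a precedence sentence would mostly repeat Section 7.4.2. The ranking is right, and it limits the seriousness of the point. It does not remove the conflict: the footnote gives a specific rule for this trial's own combination, and Section 7.4.5 directs sites to it.

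Four further points deserve weight.

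- **The flowchart is not available.** The box that the footnote qualifies cannot be seen and might itself refer to the protocol. The mismatch in wording is certain; how a site reading the whole algorithm would act is less so.
- **The hepatic comparison is weak support.** The hepatic algorithm carries a broader referral, "Please refer to protocol dose delay and discontinue criteria for specific details", but both referrals speak of delay and discontinuation, not resumption. The contrast shows that broader wording was to hand and little more. The finding does not depend on it.
- **Other safeguards remain.** These are the steroid condition, re-evaluation at least weekly during a delay, consultation with the Medical Monitor before restart after a nivolumab delay of more than 6 weeks, and permanent discontinuation if Grade 3 recurs on nivolumab alone.
- **Harm from a Grade 1 restart is not demonstrated.** The table itself accepts Grade 1 for other events, including Grade 2 pneumonitis. That is so, but for colitis and diarrhea the sponsor wrote the stricter threshold, and the appendix should not undercut it.

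**Conclusion.** The inconsistency is real and should be corrected. For Grade 3 diarrhea or colitis on the combination, Table 7.4.1-1 governs and requires return to baseline, while the Appendix 5 footnote permits restart at Grade 1.

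The practical effect is narrow. It reaches Arm A or Arm B rollover participants with a Grade 0 baseline who are at Grade 1 when restart is considered, at a site that follows the footnote. The documents give no frequency for this group, so its size is left unstated. The response-rate estimates, their precision and the sample size do not change.

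The conclusion rests on the footnote text alone, because the flowchart is not shown, and on a baseline of Grade 0 or 1 for the statement that the footnote is the laxer rule.

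**What to change.** Reword the footnote to say: *nivolumab alone can be restarted once the event has returned to baseline (see Table 7.4.1-1)*. Add a sentence to the Appendix 5 introduction stating that Table 7.4.1-1 governs delay, resumption and discontinuation wherever the two differ.

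If the footnote must stay identical to the Investigator Brochure algorithm, the precedence sentence is enough by itself. If the sponsor in fact intends Grade 1 as the threshold, the table row should be changed instead, with a clinical reason given.

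The cost is one footnote, one sentence and a short note to sites. Design, analysis and sample size are untouched.
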